2. LIST OF ABBREVIATIONS

| Term | Definition / description |
|--------------------|--|
| AE | Adverse event |
| AESI | Adverse events of special interest |
| ALQ | Above limit of quantification |
| ALT | Alanine Amino Transferase |
| AML | Acute Myelogenous Leukemia |
| AST | Aspartate Amino Transferase |
| ATC classification | Anatomical, Therapeutic, Chemical classification |
| BI | Boehringer Ingelheim |
| BLQ | Below limit of quantification |
| BLRM | Bayesian logistic regression model |
| BMI | Body Mass Index |
| BSA | Body Surface Area |
| CR | Complete Response |
| CT | Concomitant therapy |
| CTCAE | Common Terminology Criteria for Adverse Events |
| CTP | Clinical Trial Protocol |
| CTR | Clinical Trial Report |
| DBL | Data base lock |
| DILI | Drug Induced Liver Injury |
| DLT | Dose Limiting Toxicity |
| ECG | Electrocardiogram |
| eCRF | Electronic case report form |
| EFS | Event free survival |
| HI | Hematologic improvement |
| HI-E | Hematologic improvement erythroid |
| HI-N | Hematologic improvement neutrophils |
| HI-P | Hematologic improvement platelets |
| ICH | International Conference on Harmonisation |

| Term | Definition / description |
|--------|--|
| iPD | Important Protocol Deviation |
| IRR | Infusion related reaction |
| LLOQ | Lower limit of quantification |
| mCR | Marrow Complete Response |
| MedDRA | Medical Dictionary for Regulatory Activities |
| mL | Millilitre |
| MQRM | Medical and Quality Review Meeting |
| MTD | Maximum tolerated dose |
| OR | Objective response |
| PD | Progressive disease |
| PR | Partial response |
| PT | Preferred term |
| RBC TI | Red Blood Cell Transfusion Independence |
| REP | Residual effect period |
| RP2D | Recommended phase 2 dose |
| RPM | Report planning meeting |
| SAE | Serious adverse event |
| SD | Standard deviation |
| SMQ | Standardized MedDRA Queries |
| SOC | System organ class |
| SS | Screened set |
| TLS | Tumor Lysis Syndrome |
| TS | Treated set |
| ULN | Upper Limit of Normal |
| ULOQ | Upper limit of quantification |
| WHO DD | World Health Organization Drug Dictionary |

3. INTRODUCTION

As per International Conference on Harmonisation E9 (ICH E9) ([1](#)), the purpose of this document is to provide a more technical and detailed elaboration of the principal features of the analysis described in the protocol, and to include detailed procedures for executing the statistical analysis of the primary and secondary variables and other data.

This Trial Statistical Analysis Plan (TSAP) assumes familiarity with the Clinical Trial Protocol (CTP), including Protocol Amendments. In particular, the TSAP is based on the planned analysis specification as written in CTP section 7 "Statistical Methods and Determination of Sample Size". Therefore, TSAP readers may consult the CTP for more background information on the study, e.g., on study objectives, study design and population, treatments, definition of measurements and variables, planning of sample size, randomization. This TSAP follows the Boehringer Ingelheim (BI) internal reference ([2](#)).

This TSAP is based on the Project Statistical Analysis Plan wherever possible. Wordings like "randomization (first administration of study treatment in non-randomized trials)" should therefore be interpreted as applicable.

SAS version 9.4 (or later) will be used for all other analyses.

4. CHANGES IN THE PLANNED ANALYSIS OF THE STUDY

4.1 CLARIFICATIONS

As stated in the CTP, one of the Phase I primary endpoints is “occurrence of dose limiting toxicity (DLT)”. To clarify, this is defined as the number of patients with DLTs during the maximum tolerated dose (MTD) evaluation period.

4.2 CHANGES

This study was terminated prematurely during the Phase I expansion cohort stage. No patients were recruited for the Phase II part of the study. Therefore none of the Phase II analyses stated in the CTP will be performed. The rest of this TSAP specifies analyses pertaining to Phase I part of the study only.

5. ENDPOINTS

This study is an open label Phase I/II trial of BI 836858 in patients with low or intermediate-1 risk myelodysplastic syndromes. Only the Phase I part is conducted; the study is terminated with recruitment discontinued before the commencement of the Phase II part.

Phase I consists of a single arm, dose escalation stage followed by an expansion cohort stage. Dose-escalation is guided by a Bayesian logistic regression model with overdose control. The primary objectives are determination of the MTD and the recommended phase II dose (RP2D). After determination of the MTD/RP2D, two expansion cohorts—untreated or pre-treated with HMA and/or lenalidomide—are enrolled at the selected dose.

5.1 PRIMARY ENDPOINTS

The primary endpoints in the Phase I part of the trial are the MTD and the number of patients with dose limiting toxicities (DLTs) during the MTD evaluation period.

Maximum tolerated dose (MTD) and number of patients with DLTs during the MTD evaluation period:

The MTD is defined as the highest dose of BI 836858 with less than 25% risk of the true DLT rate being above 33% during the MTD evaluation period. The other primary endpoint, the number of patients with DLTs during the MTD evaluation period will be used to determine the MTD.

MTD evaluation period:

The MTD evaluation period is defined as the time from the first administration of trial medication to start of the third administration of BI 836858, excluding the day of the third administration of BI 836858. In case the third infusion of BI 836858 is not administered, the evaluation period ends 30 days after the last administration.

In case a patient has not completed the required number of administrations due to BI 836858 related toxicity, he/she will not be replaced and this will be considered as DLT. However, patients who have not completed the required number of administrations of BI 836858 for reasons other than BI 836858 related toxicity will be replaced. Patients who were replaced during the MTD evaluation period will not be considered for MTD evaluation. That is, a patient will be considered evaluable for MTD assessment if he/she received at least 2 administrations of BI 836858 or if he/she received less than 2 administrations due to DLT.

The MTD estimate after the dose escalation part of the trial will be obtained on the basis of DLTs observed during the MTD evaluation period. However, for those patients who receive more than one cycle of the treatment, all AEs that constitute a DLT will be considered in the final determination of the dose recommended for the Phase II part.

As part of this additional analysis the probabilities of the Bayesian 2-parameter logistic regression model with overdose control will be also computed including all considered DLTs.

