6. GENERAL ANALYSIS DEFINITIONS

6.1 TREATMENTS

In the Phase I part, treatments are not randomized (open-label, dose escalation). Different dose levels (planned and intermediate) of the investigational medicinal product will be evaluated. The data will be presented for all dose cohorts separately, in particular, patients will be analysed by the treatment group initially assigned in the first treatment course. In addition, totals over all dose cohorts will be given.

“Analysing treatment periods” will be used for reporting of treatment emergent adverse events (AE) and to differentiate between screening, on-treatment, post-treatment and post-study safety data. The inequalities start date \leq onset date of AE $<$ stop date will determine whether the AE will be assigned to the “analysing treatment period” or not. Table 6.1:1 defines the “analysing treatment periods” which will be used for reporting of treatment emergent AEs and safety laboratory parameters.

Table 6.1:1 Definition of analysing treatment periods

| Analysing treatment period | Start date (including) | Stop date (excluding) |
|----------------------------|---|---|
| Screening | Date of informed consent | Date of first administration of trial medication |
| MTD evaluation period | Date of first administration of trial medication | Date of third infusion or (if the third infusion was not administered) Date of first administration of trial medication + 28 days |
| On-treatment | Date of first administration of trial medication | Start date of ‘Follow-up’ |
| Follow-up | Date of end of REP +1 day, i.e. Date of last administration of trial medication + 30 days of REP + 1 day | Start date of ‘Post-study’ |
| Post-study | Last date patient status obtained / last date patient known to be alive + 1 (if patient is lost to follow-up) / date of refusal + 1 day / the date patient died + 1 | DBL + 1 day |

Data recorded between the first administration of trial medication until up to 30 days (Residual effect period; REP) after the last administration of trial medication will be considered as on-treatment.

In addition, to justify the MTD determination, AEs occurring during the MTD evaluation period will be presented separately from those occurring during the complete on-treatment period.

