7.4 PRIMARY ENDPOINTS

The primary endpoints are the MTD and the number of patients with dose limiting toxicities (DLTs) during the MTD evaluation period. The MTD is determined from the number of non-replaced patients with DLT during the MTD evaluation period (for the definition of MTD evaluation period refer to [Section 5.1](#)).

An overall summary of patients with DLT(s) which occurred during the MTD evaluation period and the on-treatment period will be provided for each dose cohort.

Patients who were treated but replaced will be not considered for the MTD determination. However, all information, including adverse events qualifying for a DLT from later times, will be considered in the final determination of the recommended Phase II dose (RP2D).

The analysis of the MTD is based on a Bayesian logistic regression model (BLRM). The MTD is defined as the highest dose for a given schedule that is expected to cause less than 25% risk of the true DLT rate being above or equal to 33% during the MTD evaluation period. Estimation of the MTD during the dose escalation phase of the study will be based upon the estimation of the posterior probability of the incidence of DLT in toxicity categories during the MTD evaluation period for all evaluable patients. The model to be used is specified in CTP section 7.

Tables and bar charts will be produced to display, for each dose level, the posterior probabilities that the true DLT rate being in the underdosing [0, 0.16), target-dosing [0.16, 0.33) and overdosing [0.33, 1] intervals.

In order to describe the occurred dose escalation steps, a listing of all treated patients will be provided. This will include the initial dose of BI 836858, patient number, treatment start date, DLT in MTD evaluation period [y/n], evaluable for MTD [y/n]. The listing will be sorted by treatment start date.

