7.8.1 Adverse events

7.8.1.1 Maximum tolerated dose and dose limiting toxicity

Analysis of MTD will be reported as described in Section 7.4.

In addition, tables displaying DLTs by primary system organ class and preferred term will be provided by initial treatment for the MTD evaluation period for the MTD evaluation set as well as for the treated set over the on-treatment period.

The purpose of these tables is to summarize and document the data that led to the selection of MTD. A summary of the number of patients with DLT within the MTD evaluation period (treatment course 1) and for all treatment courses of the on-treatment period will be given by initial treatment for the treated set.

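### SAP 5.1 and SAP Table 6.1:1 end the same MTD evaluation period on different days when no third infusion is given, so a DLT in the primary count can be missing from the AE presentation meant to justify the MTD

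*SAP*

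**What the plan says.** SAP 5.1 starts the MTD evaluation period at the first administration and ends it before the day of the third. Its fallback rule is: "In case the third infusion of BI 836858 is not administered, the evaluation period ends 30 days after the last administration".

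SAP 6.1, Table 6.1:1, defines a period of the same name. Its stop date, in a column headed as excluded, is: "Date of third infusion or (if the third infusion was not administered) Date of first administration of trial medication + 28 days". The table's scope is given as periods "which will be used for reporting of treatment emergent AEs and safety laboratory parameters". Below it, SAP 6.1 adds that "to justify the MTD determination, AEs occurring during the MTD evaluation period will be presented separately" from those of the full on-treatment period.

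SAP 7.4 points to Section 5.1 for the primary analysis ("for the definition of MTD evaluation period refer to" Section 5.1). It also plans two outputs that matter here:

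- "An overall summary of patients with DLT(s) which occurred during the MTD evaluation period and the on-treatment period will be provided" per dose cohort.
- A per-patient listing whose fields include "DLT in MTD evaluation period [y/n], evaluable for MTD [y/n".

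SAP 7.8.1.1 opens with "Analysis of MTD will be reported as described in Section 7.4". It then plans DLT tables for the MTD evaluation period and for the on-treatment period, and in one place labels the former as treatment course 1.

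In the protocol, DLTs for escalation are assessed on Cycle 1, two administrations over 28 days (4.1.3). The model parameter is the probability of a DLT in the first cycle (7.1), and the MTD rests on first-cycle DLTs (7.3.1.1).

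**The concern.** One named period, on which a primary endpoint depends, has two end dates, and each is in use for a different output. The two rules agree whenever a third infusion is given, since both stop before that day. They part only for patients who never receive it. A patient with two infusions and no third is still evaluable under SAP 5.1, so such a patient contributes to the DLT count.

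For that patient, a DLT arising after Day 28 but within 30 days of the second infusion counts toward the MTD. It is left out of the AE presentation that SAP 6.1 says exists to justify the MTD. A reader comparing the two would find a DLT in the model with no matching event in its stated support.

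The 5.1 fallback also runs past the protocol's Cycle 1 basis. SAP 4.1 says DLTs are counted over the MTD evaluation period but gives no end date. SAP 4.2 records only the early termination and the dropped Phase II analyses.

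**Working it through.** **Inputs.** Day 1 is the first administration. Planned infusions fall on Days 1 and 15 of a 28-day cycle (protocol Flow Chart 1 notes). The end rules are those of SAP 5.1 and Table 6.1:1. Patient numbers come from the protocol synopsis.

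**Formulas, no third infusion.**

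- SAP 5.1: end day = day of last infusion + 30.
- Table 6.1:1: stop day = 1 + 28 = Day 29, excluded, so the last counted day is Day 28.
- Gap = (last infusion day + 30) - 28.

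| Infusions received | SAP 5.1 end | Table 6.1:1 last day | Gap |
|---|---|---|---|
| Days 1 and 15 | 15 + 30 = 45 | 28 | Days 29-45, 17 days |
| Days 1 and 22 (assumed delay) | 22 + 30 = 52 | 28 | Days 29-52, 24 days |
| Day 1 only | 1 + 30 = 31 | 28 | Days 29-31, 3 days |

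Each gap is one day shorter if the 5.1 end day is itself excluded, which SAP 5.1 does not say. Last + 30 always exceeds first + 28, so the mismatch runs one way only: events in the primary count but outside the table's window.

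**Who can be affected.** In the one-infusion row the DLT count cannot change. Under SAP 5.1 that patient is either replaced or already counted as a DLT. The mismatch matters only with exactly two infusions. The ceiling is 21 + 6 = 27 Phase I patients; the number with exactly two infusions is not in the documents.

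**Protocol passages that are not confined to Days 1-28.** Protocol 3.1 requires observation for at least one cycle. Protocol 5.2.1.1 counts as a DLT a Cycle 2 not started until the 57th day because of a drug-related AE. For infusions on Days 1 and 15 and no third, Day 57 lies after both end dates (28 and 45).

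**What one extra DLT does to the model.** This shows the effect of the choice of window, not of the mismatch between outputs. The model of protocol 7.1 (three-component prior of Table 7.1:1, reference dose 160 mg) was integrated on a grid. Reproduction of the protocol's own probabilities that the DLT rate is at least 33%:

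| Case | Recomputed | Protocol |
|---|---|---|
| Prior, 20 / 40 / 80 / 320 mg | 0.067 / 0.091 / 0.136 / 0.443 | 0.069 / 0.091 / 0.138 / 0.441 |
| Prior, 160 mg (depends slightly on the grid) | 0.244 to 0.247 | 0.244 |
| Table 10.3:1 scenario 2, 20 mg | 0.213 | 0.222 |
| Scenario 5, 40 mg | 0.092 | 0.102 |
| Scenario 8, 320 mg | 0.209 | 0.219 |
| Scenario 9, 320 mg | 0.702 | 0.709 |

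Agreement is within about 0.01. Then, assuming 0/3 at each of 20, 40, 80 and 160 mg, the same probability at 320 mg is:

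- 0/3: 0.030; 1/3: 0.264, which crosses the 0.25 limit.
- 0/6: 0.007; 1/6: 0.080, which does not cross it.

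**The case against.** The case for treating this as wording only has real substance.

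- **The event is not lost.** It appears in the on-treatment DLT summary and, under 5.1, in the 7.4 listing. It would also be in the on-treatment DLT tables of SAP 7.8.1.1 and, as an AE of special interest, in the tables of 7.8.1.2. The 7.8.1.1 tables for the MTD evaluation period can be read as using the 5.1 window, because that section defers to 7.4. This stands and limits the weight. The reading is not secure, though: the deferral covers the MTD analysis, the same section uses the treatment course 1 label, and 7.8.1.2 sends the reader to Section 6.1.
- **A wider model run is already planned.** SAP 5.1 adds a run on all DLTs considered. True, but it brings in later-cycle events and so does not isolate the two end dates.
- **The protocol's cycle has no fixed Day 28 end.** Twenty-eight days is a planned duration, and visits are recalculated when Visit 1 of a cycle is delayed. If the third infusion is late, both SAP rules pass Day 28. Thirty days also matches the protocol's residual effect period, and DLTs are monitored beyond Cycle 1. This stands: the departure from the protocol is a matter for disclosure, not proof that 5.1 is mistaken.
- **The model figures rest on assumed data and measure window choice.** Agreed; they show only that one DLT can matter in cohorts of this size.

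None of these points makes the two end dates agree.

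**Conclusion.** The concern holds. Followed exactly, the SAP builds the primary DLT count and its stated AE justification on different windows for any patient with exactly two infusions. The gap is 17 days on the planned schedule (16 under the exclusive reading of 5.1) and grows by one day for each day the second infusion is late.

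The primary analysis itself is unambiguous, because 7.4 names 5.1. The consequence is an internally inconsistent report, of minor to moderate weight, and it should be fixed because it concerns the period that defines a primary endpoint. It becomes visible only if an evaluable two-infusion patient had a DLT with onset between the two end dates, and the documents do not show whether any did. They also do not say which end date was intended, and this review does not choose between them.

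**What to change.** - Reconcile SAP 5.1, Table 6.1:1 and the treatment course 1 label in 7.8.1.1 to one end date, with a statement of whether the end day is included. Use it for both the DLT count and the AE tables.
- Record in SAP 4.2 any departure from the protocol's Cycle 1 (28-day) basis, and state how the one-cycle observation rule and the 57th-day criterion relate to the chosen window.
- List any DLT with onset between the two end dates. Rerun the Bayesian model under the other window only if that listing is not empty.

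The cost is a few lines of SAP text and one short listing, plus a second model run only if needed. No new data are required.

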6.3 PATIENT SETS ANALYSED

The following patient sets are defined for the Phase I part:

- Screened set (SS): This patient set includes all patients who have signed the informed consent. The SS will be used for patient disposition tables.
- Treated set (TS): This patient set includes all patients who were documented to have received at least one dose of trial medication.
- MTD evaluation set: The MTD evaluation set includes all patients from the TS who have not been replaced for the MTD evaluation. Rules for replacement of patients are defined in [Section 5.1](#) and CTP section 3.3.4.1.

The MTD evaluation set will be used for the primary endpoint analyses whereas the TS will be used for all other efficacy and safety analyses in the Phase I part. The list of replaced patients will be provided by the clinical trial monitor no later than at the last RPM and will be attached to the RPM minutes.

No per protocol population will be used for analyses.

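### The replacement rule in SAP 5.1 can drop an observed DLT from the primary MTD model, and it conflicts with the evaluability sentence in the same section (minor)

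*SAP*

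**What the plan says.** Three parts of SAP 5.1 bear on who counts towards the MTD.

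- **Replacement.** Patients who do not complete the required administrations "for reasons other than BI 836858 related toxicity will be replaced". Those who stop because of drug-related toxicity are not replaced and count as DLTs.
- **Exclusion.** "Patients who were replaced during the MTD evaluation period will not be considered for MTD evaluation".
- **Evaluability.** The closing sentence, offered as a restatement, makes a patient evaluable after at least two administrations, or if he or she "received less than 2 administrations due to DLT". It sets no attribution condition.

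SAP 6.3 then defines the MTD evaluation set, used for the primary endpoints, as one that "includes all patients from the TS who have not been replaced for the MTD evaluation". SAP 7.4 says: "The MTD is determined from the number of non-replaced patients with DLT during the MTD evaluation period", and "Patients who were treated but replaced will be not considered for the MTD determination". None of these sections makes an exception for a replaced patient who has already had a DLT.

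On the protocol side, section 5.2.1.1 defines the first type of DLT as a Grade 3 or higher non-hematologic event that is not disease-related. Drug attribution is not a condition there, although it is in the criterion on failing to deliver the full cycle 1 dose. Section 4.1.4 requires dosing to be held after any DLT. Section 3.3.4.1 contains the same attribution-based replacement rule, but does not say that a replaced patient's DLT leaves the model.

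**The concern.** Replacement depends on whether toxicity was attributed to the drug; a DLT need not be. Two kinds of patient fall into the gap.

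(a) A DLT judged unrelated to BI 836858 stops dosing before infusion 2. The replacement and exclusion sentences remove the patient, while the evaluability sentence keeps the patient. Two programmers could build different MTD evaluation sets from the same data.

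(b) A patient has a DLT after infusion 1 and misses infusion 2 for some other reason, such as withdrawal of consent. The patient has fewer than two administrations, and not because of the DLT, so is excluded under both sentences.

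The number of patients with DLTs is a primary endpoint and the only outcome in the Bayesian logistic regression model (BLRM). A patient with a DLT is informative however many infusions were given, and removing one can only lower the counted DLT rate. Excluding DLT-free patients with too little exposure is reasonable and is not questioned here.

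**Working it through.** **The rules applied to each patient type**

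| Patient with fewer than 2 infusions | Replacement and exclusion sentences | Evaluability sentence |
|---|---|---|
| Stopped by drug-related DLT | kept | kept |
| Stopped by DLT judged unrelated | excluded | kept |
| DLT, infusion 2 missed for another reason | excluded | excluded |
| No DLT, other reason | excluded | excluded |

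Row 2 is the conflict. Row 3 is the consistent loss of a DLT. SAP 6.3 and 7.4 are worded in terms of replacement, so they follow the middle column.

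**Inputs for the size of the effect**

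- Model (protocol 7.1): logit p(d) = log α + β·log(d/160).
- Prior on (log α, log β) (protocol Table 7.1: 1): weights 0.90, 0.05, 0.05; means (−2.189, 0.146), (−0.549, −0.233), (−4.068, −1.372); SDs (2, 1), (2, 1), (5, 0.01); correlations 0.
- Limit: a dose qualifies if P(OD) = P(p(d) ≥ 0.33 | data) < 0.25.
- Patients (protocol synopsis): 21 in escalation and 6 in expansion, 27 in all. Patients and DLTs per dose are not given, so the allocations below are assumed.

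The posterior is proportional to the prior times the product over doses of p^x·(1−p)^(n−x), integrated numerically on a grid.

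**Reproducing the plan's figures.** Prior P(OD) at 20, 40, 80, 160 and 320 mg came out at 0.067, 0.091, 0.136, 0.245 and 0.443, against 0.069, 0.091, 0.138, 0.244 and 0.441 in protocol Table 7.1: 2. For Table 10.3: 1, scenario 8 at 320 mg gave 0.209 against 0.219, and scenario 9 gave 0.702 against 0.709.

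**Contrast.** The patient with the DLT is kept alongside the replacement, or dropped.

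Assume 0/3 at each of 20, 40, 80 and 160 mg (12 patients) and the rest at 320 mg:

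| Total | Kept | P(OD) at 320 mg | Dropped | P(OD) at 320 mg | Status changes? |
|---|---|---|---|---|---|
| 12 + 9 = 21 | 2/9 | 0.124 | 1/8 | 0.037 | no |
| 21 | 3/9 | 0.337 | 2/8 | 0.169 | **yes** |
| 21 | 4/9 | 0.611 | 3/8 | 0.424 | no |
| 12 + 15 = 27 | 4/15 | 0.186 | 3/14 | 0.092 | no |
| 27 | 5/15 | 0.372 | 4/14 | 0.234 | **yes** |
| 27 | 6/15 | 0.588 | 5/14 | 0.441 | no |

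Other assumed allocations of 27 patients:

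- 0/3 at 20–80 mg, 0/6 at 160 mg, 12 at 320 mg (9 + 6 + 12): changes only at 4/12 against 3/11, 0.329 against 0.183.
- 0/3 at 20–80 mg, 160 mg as top dose with 18 patients (9 + 18): changes only at 6/18 against 5/17, about 0.33 against 0.21.
- 0/3 at 20–80 mg, 1/6 at 160 mg, 12 at 320 mg: never changes. 3/12 against 2/11 is 0.210 against 0.103, and 4/12 against 3/11 is 0.416 against 0.265.
- 0/4 at each of 20–160 mg, 11 at 320 mg (16 + 11): never changes. 3/11 against 2/10 is 0.197 against 0.084, and 4/11 against 3/10 is 0.424 against 0.255.

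In each allocation at most one DLT count puts the top dose on different sides of the limit.

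**The case against.** The strongest reply has four parts.

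**The DLT is not lost.** SAP 7.4 follows its exclusion sentence by saying that everything known, including later DLT-qualifying events, feeds the final choice of the recommended Phase II dose. SAP 5.1 adds a second BLRM using all considered DLTs. SAP 7.8.1.1 plans "A summary of the number of patients with DLT within the MTD evaluation period" on the treated set, SAP 7.4 lists every treated patient with DLT and evaluability flags, and SAP 7.8 lists replaced patients. This stands as disclosure. A reader might infer that the DLT disappears from the report or from dose selection; the documents do not support that. What remains is that the first safeguard concerns the recommended dose and not the MTD. The additional BLRM is introduced "for those patients who receive more than one cycle of the treatment"; it may include a replaced patient's DLT, but the text does not say so. Neither corrects the primary MTD probabilities.

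**The evaluability sentence settles case (a).** As the closing restatement it can be taken as the operative definition, and a programmer following it keeps the patient. That is a workable reading, but SAP 6.3 and 7.4 are written in terms of replacement, so it is not the only one.

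**Case (b) is rare.** It needs a DLT between the first two infusions and an unrelated reason for missing the second. Because protocol 4.1.4 forces a hold after any DLT, the missed infusion would usually be due to the DLT itself. This is accepted.

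**The protocol does not clearly forbid the exclusion.** Protocol 3.1 treats a DLT as completing a patient's observation, but that governs when the model is updated. Protocol 7.3.3 puts a descriptive MTD evaluation on the Phase I treated set, which does not define the BLRM population. A reader might infer that the SAP breaches the protocol; the text supports only that the protocol does not require an observed DLT to be dropped.

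**Conclusion.** The point holds as a minor defect in the wording of a primary-endpoint rule. SAP 5.1, 6.3 and 7.4 can omit an observed DLT from the primary MTD posterior: ambiguously when a DLT judged unrelated stops dosing, and consistently, though less often, when infusion 2 is missed for another reason. Any resulting error runs towards making the drug look safer.

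The numerical effect rests on assumed allocations. In those tried, no more than one DLT count per allocation changes whether the top dose meets the 0.25 limit, and in two of them none does. In the changes shown, the kept DLT rate at the top dose is 33% (3/9, 5/15, 4/12, 6/18), at the edge of the overdose interval.

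A reader might go further and infer that the reported MTD is wrong or that patients were dosed on a biased model. The documents show no affected patient. The SAP was finalised in January 2020, after recruitment had stopped, so no escalation decision used this wording, and no Phase II follows.

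**What to change.** State in SAP 5.1, with matching wording in 6.3 and 7.4, that any patient with a DLT per protocol 5.2.1.1 in the MTD evaluation period is evaluable and stays in the MTD evaluation set, whatever the attribution, the number of administrations or the reason for stopping, and even if a replacement was enrolled. Only DLT-free patients with fewer than two administrations are excluded.

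The cost is one sentence and two conforming edits. No new data, additional analysis or protocol amendment is needed.
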